5.2.1. Derivations and Handling of Missing Baseline Data

Definition	Reporting Details
Change from Baseline	= Post-Dose Visit Value – Baseline
% Change from Baseline	= $100 \times [(Post-Dose Visit Value - Baseline) / Baseline]$
Maximum Change from Baseline	= Calculate the change from baseline at each given timepoint and determine the maximum change

NOTES :

- Unless otherwise specified, the baseline definitions specified in Section 5.2 Baseline Definitions will be used for derivations for endpoints / parameters and indicated on summaries and listings.
- Unless otherwise stated, if baseline data is missing no derivation will be performed and will be set to missing.
- The baseline definition will be footnoted on all change from baseline displays.

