11.3. Appendix 3: Assessment Windows**11.3.1. Definitions of Assessment Windows for Analyses**

Nominal time will be used for all analysis except PK analysis where planned and actual time will be used.

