11.5.2. Reporting Standards

Reporting Standards	
General	

 The current GSK Integrated Data Standards Library (IDSL) will be applied for reporting, unless otherwise stated: 
 4.03 to 4.23: General Principles 5.01 to 5.08: Principles Related to Data Listings 6.01 to 6.11: Principles Related to Summary Tables 7.01 to 7.13: Principles Related to Graphics 	
Formats	

 All data will be reported according to the actual treatment the participant received unless otherwise stated. GSK IDSL Statistical Principles (5.03 & 6.06.3) for decimal places (DP's) will be adopted for reporting of data based on the raw data collected. Numeric data will be reported at the precision collected on the eCRF. The reported precision from non eCRF sources will follow the IDSL statistical principles but may be adjusted to a clinically interpretable number of DP's. 	
Planned and Actual Time	

 Reporting for tables, figures and formal statistical analyses: 
 Planned time relative to dosing will be used in figures, summaries, statistical analyses and calculation of any derived parameters, unless otherwise stated. The impact of any major deviation from the planned assessment times and/or scheduled visit days on the analyses and interpretation of the results will be assessed as appropriate. Reporting for Data Listings: 
 Planned and actual time relative to study drug dosing will be shown in listings (Refer to IDSL Statistical Principle 5.05.1). Unscheduled or unplanned readings will be presented within the participant's listings. 	

Reporting Standards	

 Visits outside the protocol defined time-windows (i.e. recorded as protocol deviations) will be included in listings but omitted from figures, summaries and statistical analyses. 	
Unscheduled Visits	

 Unscheduled visits will not be included in summary tables. Unscheduled visits will not be included in figures. All unscheduled visits will be included in listings. 	
Descriptive Summary Statistics	
Continuous Data	Refer to IDSL Statistical Principle 6.06.1
Categorical Data	N, n, frequency, %
Reporting of Pharmacokinetic Concentration Data	
Descriptive Summary Statistics	Refer to IDSL Statistical Principle 6.06.1 Assign zero to NQ values (Refer to GUI_51487 for further details)

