11.6. Appendix 6: Derived and Transformed Data

11.6.1. General

Multiple Measurements at One Time Point

 Mean of the measurements will be calculated and used in any derivation of summary statistics but if listed, all data will be presented. If there are two values within a time window the value closest to the target day for that window will be used. If values are the same distance from the target then the mean will be taken. Participants with both High and Low values for Normal Ranges at any post-baseline visits for safety parameters will be counted in both the High and Low categories of “Any visit post-baseline” row of related summary tables. This will also be applicable to relevant Potential Clinical Importance summary tables.
Study Day

 Calculated as the number of days from randomisation date: 
 Ref Date = Missing → Study Day = Missing Ref Date < Randomisation Date → Study Day = Ref Date – Randomisation Date Ref Date ≥ Randomisation Date → Study Day = Ref Date – (Randomisation Date) + 1

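### SAP 11.5.2 makes no exception for maximum and worst-case tables, so they can miss an off-schedule extreme; separately, cTnI and BNP values have no unconditional listing

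*SAP*

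**What the plan says.** **Unscheduled data.** SAP 11.5.2 states "Unscheduled visits will not be included in summary tables", bars such visits from figures as well, and adds "All unscheduled visits will be included in listings". For measurements as distinct from visits it says only that "Unscheduled or unplanned readings will be presented within" the participant's listings; it is silent on whether they may enter tables.

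**Time basis.** The same section says "Planned time relative to dosing will be used in figures, summaries, statistical analyses and calculation of any derived parameters", subject to an unless-otherwise-stated clause. SAP 11.3.1 says "Nominal time will be used for all analysis except PK analysis where planned and actual time will be used". SAP 5.2.1 defines the maximum change from baseline as follows: "Calculate the change from baseline at each given timepoint and determine the maximum change".

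**Several values together.** SAP 11.6.1 averages measurements at one time point, and adds "If there are two values within a time window the value closest to the target day for that window will be used".

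**Tables of extremes.** SAP 11.10.5 plans six: worst-case chemistry (2.11), haematology (2.13), urinalysis (2.16) and vital signs (2.27), maximum QTc (2.21) and maximum QTc increase (2.24). No programming note for them mentions unscheduled data.

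**cTnI and BNP.** Protocol Table 15 places both under clinical chemistry. SAP 11.8.1 gives neither a PCI criterion. The laboratory listings are Listings 20 to 23 in SAP 11.10.10. By contrast, ECG and vital signs have all-value listings (28, 29, 33, 34).

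**The concern.** A reader takes maximum and worst case to mean the subject's true extreme after dosing. The protocol foresees off-schedule safety data: section 9 allows repeat or unscheduled samples, 9.4.4 asks for a 12-lead ECG to confirm an abnormal finding on continuous monitoring, and 8.1.4 requires a repeat cTn or BNP above set thresholds. Such readings tend to come from subjects who already show an abnormality. If they are left out, any error runs toward normal, and it falls on the primary objective, which is safety.

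The cTnI/BNP point has a different cause. Monitoring these markers is a named mitigation for the nonclinical cardiac findings (protocol 3.3.1), yet the planned outputs may not show a subject's individual values at all.

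**Working it through.** No figure in the plan needs reproducing. The check traces the rules through the planned displays, with simple proportions for size.

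**1. Can an extra reading reach a table of extremes?**
- If it counts as an unscheduled visit, 11.5.2 excludes it outright.
- If it counts only as a reading on a scheduled inpatient day, 11.5.2 mentions it for listings alone. Summaries and derived parameters use planned time, and 11.3.1 uses nominal time for all non-PK analysis. An extra reading has neither. The definition in 5.2.1 bears on Table 2.24 but not on 2.21, and it does not say whether an extra reading supplies a timepoint.
- If it is assigned to a window, 11.6.1 keeps the value nearest the target, or the mean if tied. Neither rule preserves the extreme.
- The 11.6.1 bullet on "Participants with both High and Low values for Normal Ranges at any post-baseline visits for safety parameters" counts a subject in both categories but does not mention unscheduled data.

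No branch gives a stated route in.

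**2. When would a table change?** Only when the off-schedule reading falls in a worse category than every scheduled one.
- QTc (SAP 11.8.2): a subject whose scheduled values are all at or below 450 msec, with a single off-schedule value in the 480 to 499 band, would be tabulated as not above 450.
- Normal-range tables: a repeat after a scheduled High cannot alter the category, so the extreme must first appear off schedule.

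**3. Opportunity.** Protocol 2.1 times ECGs at 0.5, 6, 12 and 24 h within the 24 h post-dose monitoring period. The gaps are 6 − 0.5 = 5.5 h, 12 − 6 = 6 h and 24 − 12 = 12 h. A confirmatory ECG is off schedule unless it coincides with one of those times.

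**4. Size for one subject.** The inputs are 6 active and 2 placebo in each of Cohorts 1 and 2 (protocol 10.2.1), one active and one placebo sentinel in Cohort 3 (protocol 5.1.1; SAP 1), and placebo pooled by part (SAP 5.1, note 3). Planned placebo is 2 + 2 + 1 = 5, and the planned total is 6 + 6 + 1 + 5 = 18.

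| Column | Planned n | One subject moved (percentage points) |
|---|---|---|
| 0.1 mg | 6 | 1/6 = 16.7 |
| 0.25 mg | 6 | 1/6 = 16.7 |
| 1.3 mg | 1 | 1/1 = 100 |
| Placebo | 5 | 1/5 = 20 |

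**5. cTnI and BNP.** The rows in 11.8.1 are 6 haematology + 9 chemistry + 5 liver = 20, and none is for either marker. The laboratory listings run as follows:
- Listing 20: all laboratory data, but only for subjects with a PCI value.
- Listing 21: PCI values only.
- Listing 22: character (dipstick) results.
- Listing 23: urinalysis.

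So 0 of 4 show numeric chemistry without a PCI filter. A cTnI or BNP value cannot itself trigger Listing 20 or 21. It appears in Listing 20 only if the same subject has a PCI value on another analyte. This holds for scheduled and unscheduled values alike. Scheduled values can still enter Tables 2.9 and 2.11 as grouped data.

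**The case against.** The best reply is that the exclusion is partly inferred. The SAP uses the words visit and reading separately and bars only visits from tables. Part A subjects were inpatients, so an extra ECG need not be an unscheduled visit. A per-subject maximum is not indexed by time, the planned-time rule has its own exception clause, and Tables 2.22 and 2.23 expressly admit continuous monitoring results. The sponsor's standard shells for 2.21 and 2.24 are not in the documents and might select all post-baseline records. This stands as a limit on certainty: one cannot say that the plan definitely excludes every extra reading. It does not remove the gap. The standards apply only where the SAP does not state otherwise, and no sentence lets such a reading into these six tables.

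A reader might infer that the QTc tables are more exposed than the other four. The documents do not support that. All six change on the same condition, and the alerts in protocol Appendix 9 are rate and rhythm events with no QTc threshold.

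Keeping safety ECGs out of QTc tables also has some logic, because protocol 8.1.2 exempts them from the one-formula-per-subject rule. That is a fair reason for care in the fix. It does not justify calling a table a maximum without qualification.

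The closest-to-target rule in 11.6.1 needs windows, and 11.3.1 defines none, so its practical effect cannot be judged.

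On cTnI/BNP, the clinical event is unlikely to vanish. Clinically relevant changes are recorded as adverse events (protocol 9.4.6), echocardiograms are in Listing 36, and withdrawals are in Listings 1 and 17. That stands; what can be missing is the number itself.

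**Conclusion.** The point holds as a minor reporting defect. Followed as written, the plan can produce a maximum or worst case in six tables that is not the subject's extreme, with any error toward normal. One affected subject would move a column by 17, 20 or 100 percentage points. This assumes that the planned numbers were dosed, since actual numbers are not given, and that an extra reading is handled under the planned-time rules. How many readings would change cannot be known from the documents.

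The cTnI/BNP gap is separate. It comes from 11.8.1 and the choice of listings, not from 11.5.2. It would be wrong to present it as a loss of unscheduled values only.

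A reader might go further and infer that an extreme was missed, or that the ventricular tachycardia that ended the study is obscured. Nothing supports either. No omitted value is shown, the adverse event and serious adverse event displays (Tables 2.1 to 2.8) are unaffected, and ECG and vital-sign values remain in Listings 28, 29, 33 and 34. The safety analysis is descriptive, so no inference is at stake.

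**What to change.** - In SAP 11.5.2, limit the exclusion of unscheduled visits to by-visit summaries. Limit the closest-to-target selection in 11.6.1 in the same way.
- State that the maximum and worst-case tables (2.11, 2.13, 2.16, 2.21, 2.24, 2.27) use all post-dose readings, including unscheduled ones.
- For QTc, tabulate an unscheduled ECG only where the subject's own correction formula can be derived under SAP 11.6.3. Otherwise list the reading and footnote it.
- Footnote that subjects with events contribute more readings to these tables.
- Add one listing of all cTnI and BNP values for all subjects, scheduled and unscheduled, flagged for reporting only at the thresholds already in protocol 8.1.4.

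The cost is a few sentences of SAP text, footnotes, one listing and minor programming, with no new data. There are two trade-offs: unequal numbers of readings per subject, and some ECGs that can be listed but not tabulated. The footnotes disclose both.

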11.5.3. Reporting Standards for Pharmacokinetic

Pharmacokinetic Concentration Data	
PC Windows Non-Linear (WNL) File	PC WNL file (CSV format) for the non-compartmental analysis by Clinical Pharmacology Modelling and Simulation function will be created according to the [PKOne standards] Note: Concentration values will be imputed as per GUI_51487
Descriptive Summary Statistics, Graphical Displays and Listings	Refer to IDSL PK Display Standards. Refer to IDSL Statistical Principle 6.06.1. Note: Concentration values will be imputed as per GUI_51487 for descriptive summary statistics/analysis and summarized graphical displays only.
NONMEM/Pop PK File	Not applicable.
NONMEM/PK/PD File	Not applicable.
Pharmacokinetic Parameter Derivation	
PK Parameter to be Derived by Programmer	Not applicable.
Pharmacokinetic Parameter Data	
Is NQ impacted PK Parameters Rule Being Followed	Yes, refer to SOP_3140000
Descriptive Summary Statistics, Graphical Displays and Listings	Refer to IDSL PK Display Standards.

11.6. Appendix 6: Derived and Transformed Data

11.6.1. General

Multiple Measurements at One Time Point

 Mean of the measurements will be calculated and used in any derivation of summary statistics but if listed, all data will be presented. If there are two values within a time window the value closest to the target day for that window will be used. If values are the same distance from the target then the mean will be taken. Participants with both High and Low values for Normal Ranges at any post-baseline visits for safety parameters will be counted in both the High and Low categories of “Any visit post-baseline” row of related summary tables. This will also be applicable to relevant Potential Clinical Importance summary tables.
Study Day

 Calculated as the number of days from randomisation date: 
 Ref Date = Missing → Study Day = Missing Ref Date < Randomisation Date → Study Day = Ref Date – Randomisation Date Ref Date ≥ Randomisation Date → Study Day = Ref Date – (Randomisation Date) + 1

11.6.2. Study Population

Treatment Compliance

 Treatment compliance will be calculated based on the formula: $\text{Treatment Compliance} = \text{Number of Actual Doses} / (\text{Planned Treatment Duration in Days} * \text{Frequency})$

 Frequency is 2 for BID and 1 for QD. Treatment compliance could be greater than 100% if there are events of overdose. Cumulative compliance (since Day 1) at each visit will be calculated. Planned Treatment Duration is defined as the number of days planned on study treatment. As Part A is single dose this would be one day.
Extent of Exposure

 Number of days of exposure to study drug will be calculated based on the formula: $\text{Duration of Exposure in Days} = \text{Treatment Stop Date} - (\text{Treatment Start Date}) + 1$ Participants who were randomized but did not report a treatment start date will be categorised as having zero days of exposure.
Demographics
Age

 GSK standard IDSL algorithms will be used for calculating age where birth date will be imputed as follows: 
 Any participant with a missing day will have this imputed as day ‘15’. Any participant with a missing date and month will have this imputed as ‘30th June’. Birth date will be presented in listings as ‘YYYY’.
Body Mass Index (BMI)

 Calculated as $\text{Weight (kg)} / [\text{Height (m)}^2]$

11.6.3. Safety

ECG Parameters
RR Interval

 IF RR interval (msec) is not provided directly, then RR can be derived as : 
 [1] If QTcB is machine read & QTcF is not provided, then : $RR = \left[\left(\frac{QT}{QTcB} \right)^2 \right] * 1000$ [2] If QTcF is machine read and QTcB is not provided, then: $RR = \left[\left(\frac{QT}{QTcF} \right)^3 \right] * 1000$
Corrected QT Intervals

 When not entered directly in the eCRF, corrected QT intervals by Bazett's (QTcB) and Fredericia's (QTcF) formulas will be calculated, in msec, depending on the availability of other measurements. IF RR interval (msec) is provided then missing QTcB and/or QTcF will be derived as : $QTcB = \frac{QT}{\sqrt[4]{RR}}$ $QTcF = \frac{QT}{\sqrt[3]{RR}}$

Laboratory Parameters

 If a laboratory value which is expected to have a numeric value for summary purposes, has a non-detectable level reported in the database, where the numeric value is missing, but typically a character value starting with '<x>' (or indicated as less than x in the comment field) is present, the corresponding numeric value will be imputed as $0.5 * x$</x>

11.6.4. Pharmacokinetic

PK Parameters

 Please see Table 7 for derived Pharmacokinetic parameters

11.6.5. Pharmacodynamic

PD Parameters

 The concentrations and change from baseline values (with baseline defined as the average of all pre-dose measurements (incl. Day -1)) will be summarized by planned time points.

11.7. Appendix 7: Reporting Standards for Missing Data

11.7.1. Premature Withdrawals

Element	Reporting Detail
General	
 • All participants who withdraw prematurely from the study/study drug will be documented and the reason for their withdrawal recorded in the final Clinical Pharmacology Study Report (CPSR). • Withdrawn participants may be replaced in the study except in Part A Cohorts (3-8). • All available data from participants who were withdrawn from the study will be listed and all available planned data will be included in summary tables and figures, unless otherwise specified.

11.7.2. Handling of Missing Data

Element	Reporting Detail
General	
 • Missing data occurs when any requested data is not provided, leading to blank fields on the collection instrument: 
 ○ These data will be indicated using a “blank” in participant listing displays. Unless all data for a specific visit are missing in which case the data is excluded from the table. ○ Answers such as “Not applicable” and “Not evaluable” are not considered to be missing data and should be displayed as such.
Outliers	
 • Any participants excluded from the summaries and/or statistical analyses will be documented along with the reason for exclusion in the clinical study report.

11.7.2.1. Handling of Missing and Partial Dates

Element	Reporting Detail
General	Partial dates will be displayed as captured in participant listing displays.
Adverse Events	
 • The eCRF allows for the possibility of partial dates (i.e., only month and year) to be recorded for AE start and end dates; that is, the day of the month may be missing. In such a case, the following conventions will be applied for calculating the time to onset and the duration of the event: 
 ○ Missing Start Day: First of the month will be used unless this is before the start date of study treatment; in this case the study treatment start date will be used and hence the event is considered On-treatment as per Appendix 4: Treatment States and Phases. ○ Missing Stop Day: Last day of the month will be used, unless this is after the stop date of study treatment; in this case the study treatment stop date will be used. • Completely missing start or end dates will remain missing, with no imputation applied. Consequently, time to onset and duration of such events will be

Element	Reporting Detail
	
missing.
 
 • AE time will be collected and if it is missing the following imputation will be applied: 
 ◦ If AE start time is missing then time is imputed as 00:00 unless the AE occurs on the first day of dosing in which case it has been imputed as the time of first dose. ◦ If AE end time is missing then time is imputed as 23:59. • Start or end dates which are completely missing (i.e. no year specified) will remain missing, with no imputation applied.

11.7.2.2. Handling of Partial Dates

Element	Reporting Detail
Concomitant Medications	
 • Partial dates for any concomitant medications recorded in the CRF will be imputed using the following convention: 
 ◦ If the partial date is a start date, a '01' will be used for the day and 'Jan' will be used for the month ◦ If the partial date is a stop date, a '28/29/30/31' will be used for the day (dependent on the month and year) and 'Dec' will be used for the month. • The recorded partial date will be displayed in listings.
Adverse Events	
 • Any partial dates for adverse events will be raised to data management. If the full date cannot be ascertained, the following assumptions will be made: 
 ◦ If the partial date is a start date, a '01' will be used for the day and 'Jan' will be used for the month. ◦ However, if these results in a date prior to Week 1 Day 1 and the event could possibly have occurred during treatment from the partial information, then the Week 1 Day 1 date will be assumed to be the start date. ◦ The AE will then be considered to start on-treatment (worst case). ◦ If the partial date is a stop date, a '28/29/30/31' will be used for the day (dependent on the month and year) and 'Dec' will be used for the month. • The recorded partial date will be displayed in listings.

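### SAP 11.7.2.1 and 11.7.2.2 impute the same partial adverse-event dates differently, and neither rule suits a single-bolus study

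*SAP*

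**What the plan says.** **SAP 11.7.2.1, Adverse Events.** The section first says what a partial date is on this eCRF: "The eCRF allows for the possibility of partial dates (i.e., only month and year) to be recorded for AE start and end dates", and adds "that is, the day of the month may be missing". For a missing start day: "First of the month will be used unless this is before the start date of study treatment"; otherwise the treatment start date is used. For a missing stop day: "Last day of the month will be used, unless this is after the stop date of study treatment"; otherwise the treatment stop date is used. These conventions are given for deriving time to onset and duration. At the other extreme: "Start or end dates which are completely missing (i.e. no year specified) will remain missing, with no imputation applied".

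**SAP 11.7.2.2, Adverse Events.** Any partial AE date goes first to data management. If the full date cannot be obtained: "If the partial date is a start date, a '01' will be used for the day and 'Jan' will be used for the month". If that lands before Day 1 and the event could have happened during treatment, "then the Week 1 Day 1 date will be assumed to be the start date". For a stop: "a '28/29/30/31' will be used for the day (dependent on the month and year) and 'Dec' will be used for the month". Listings show the partial date as it was recorded.

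**Related text.** SAP 11.6.2 sets the planned treatment duration in Part A at one day. SAP 11.4.2 flags an AE as treatment-emergent if it starts between treatment start and treatment stop plus 5 half-lives. The SAP does not say which of the two sections prevails.

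**The concern.** A programmer given one partial AE date has two instructions with different answers. 11.7.2.2 applies to any partial AE date and does not require the month to be missing, yet 11.7.2.1 says the month is always there. Followed to the letter, 11.7.2.2 discards a known month.

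Choosing 11.7.2.1 does not settle the matter. Its cap on the stop date presumes a treatment period long enough to contain the event. After a single bolus, treatment stop is the dosing day, so a partial stop in or after the dosing month is pulled back to that day.

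At stake are the derived onset, duration, study phase and treatment-emergent flag of AEs with incomplete dates. The trial was terminated over an event whose relationship to the drug could not be excluded, so AE timing relative to dose should have one definition.

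**Working it through.** The plan gives no figure to reproduce. The check applies each rule to the same recorded dates.

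**Inputs**
- Day may be missing, month and year recorded (SAP 11.7.2.1).
- Part A treatment start = treatment stop = dose date D (SAP 11.6.2).
- Half-life about 35 hours (Protocol 9.3), so the treatment-emergent window is 5 × 35 = 175 h = 7.3 days. Using this half-life in SAP 11.4.2 is an assumption, since the SAP gives no value there.
- Dosing dates are assumed, for illustration. Cohorts 1 and 2 were dosed between the original protocol (14 June 2017) and Amendment 3 (29 November 2017), which reports them complete, so September 2017 is a possible month. 8 February 2018 is the date the SAP introduction attaches to Cohort 3.

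**Rules, for a recorded month m**
- 11.7.2.1: start = later of (first of m, D); stop = earlier of (last of m, D).
- 11.7.2.2, filling only what is missing: start = first of m, moved to D by the Day 1 clause where that applies; stop = last of m.
- 11.7.2.2, literal: start = 1 January of the recorded year, with the same Day 1 clause; stop = 31 December.
- Duration = stop − start + 1.

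**Results, with start and stop both recorded as month and year only**

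| D (assumed) | Recorded | 11.7.2.1 | 11.7.2.2 fill-only | 11.7.2.2 literal |
|---|---|---|---|---|
| 8 Feb 2018 | Feb–Feb 2018 | 8 Feb to 8 Feb, 1 day | 8 Feb to 28 Feb, 21 days | 8 Feb to 31 Dec, 327 days |
| 25 Jan 2018 | Feb–Feb 2018 | 1 Feb to 25 Jan, −6 days | 1 Feb to 28 Feb, 28 days | 1 Jan to 31 Dec, 365 days |
| 28 Sep 2017 | Oct–Oct 2017 | 1 Oct to 28 Sep, −2 days | 1 Oct to 31 Oct, 31 days | 1 Jan to 31 Dec, 365 days |

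In the last two rows the literal start takes the Day 1 clause to cover the dosing day only.

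**What follows**
1. *Stop dates conflict under either reading.* Against 11.7.2.1, the fill-only stop is 20, 34 and 33 days later in the three rows, and the literal stop 326, 340 and 94 days later.
2. *Start dates conflict only under the literal reading, and not in the dosing month,* where the Day 1 clause gives the same answer as 11.7.2.1. In row 2 the onset is +7 days from dose under 11.7.2.1 (inside 7.3 days, so treatment-emergent) and −24 days under the literal reading (pre-dose).
3. *11.7.2.1 fails by construction when treatment lasts one day.* Its start is never before D and its stop never after D. If both dates are partial, the derived duration cannot exceed one day, and the stop precedes the start whenever the recorded start month is later than the dosing month.
4. *A start month before the dosing month* is moved to D by 11.7.2.1. This should be rare, because AE collection begins at admission on the day before dosing.

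**The case against.** **The literal reading is probably not what was meant.** The stop rule lets the day depend on the month and year, yet December always has 31 days. That makes sense only if a recorded month is kept and December fills a gap. This stands. A reader might infer that the SAP intends to overwrite known months; the wording does not support that. The contradiction remains, because on the fill-only reading the January/December clause has nothing to act on, and the stop dates still differ.

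**Onset and duration belong to 11.7.2.1.** That section claims them expressly, while 11.7.2.2 speaks of on-treatment status. On that division the year-long durations in the last column would never be derived. But those quantities then rest on the section whose stop cap fails, and 11.7.2.1 also draws an on-treatment conclusion, so the division is not clean.

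**The Day 1 clause may rescue the start.** If *during treatment* is read together with the 5 half-life window, the literal starts in rows 2 and 3 move to the dose date and stay treatment-emergent. This is a fair reading, so loss of the flag is possible but not certain.

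**AE counts do not visibly depend on the imputed date.** A reader might infer that the primary safety result is biased. The documents do not support that: SAP Tables 2.1 to 2.8 cover all, drug-related, common, serious and withdrawal AEs in All Subjects, and no title restricts to treatment-emergent events or summarises onset or duration.

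**Few records should be affected.** Partial dates are queried first, subjects are inpatients after dosing, listings show the date as recorded, and dosing ended with the Cohort 3 sentinels. This stands. Nor do the documents show that the affected events would be mainly those after discharge.

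**Conclusion.** The two sections conflict, neither is given precedence, and neither works as written for a single dose. 11.7.2.2 is either wrong (literal) or idle in its January/December clause (fill-only). 11.7.2.1 can place an AE's stop before its start.

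The consequence is minor. It is confined to derived onset, duration, study phase and the treatment-emergent flag, for the partial dates that survive data queries. Their number is unknown and probably small. The planned AE incidence tables are unlikely to change. Whether any listing displays derived onset or duration cannot be told, because the display shells are not in the SAP.

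The conclusion rests on the SAP's own statements that only the day can be missing and that Part A treatment lasts one day. The size of each discrepancy depends on the assumed dosing dates; the conflict does not.

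**What to change.** Keep one AE rule, in 11.7.2.1, and delete the Adverse Events row of 11.7.2.2, moving its query to data management into 11.7.2.1. The rule would read:

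- Keep the recorded month and impute only the day.
- Start: if the recorded month is the dosing month or later, the later of the first of that month and the dose date.
- Stop: the last day of the recorded month, but not earlier than the start. Remove the cap at treatment stop.
- Completely missing dates stay missing, as now.

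For row 2 of the table this gives 1 to 28 February 2018, 28 days.

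In the concomitant-medication row of 11.7.2.2, state that January and December are used only where the month itself is missing.

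Deleting the row is not enough, because the cap in 11.7.2.1 must go too. The cost is one deleted row, a rewritten start and stop rule, a clarifying clause and the matching programming change. No new data are needed.
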